10.1 Required Data for Study Screening

The following must be obtained within 28 days prior to the 1st day of treatment:

- Medical history, medication review, physical exam, height and weight, ECOG performance status (see Appendix A)
- CBC with differential, blood chemistries including complete metabolic panel, phosphorus, magnesium, uric acid, LDH, TSH, creatinine kinase, lipase, triglycerides. Urine studies to include a urine dipstick for blood and protein and if positive (2+ or greater for protein) a microscopic urinalysis and 24 hour urine collection (for protein).
 - For patients assigned to cohorts A2, A3, and B2 with a previous history of anthracycline treatment and who are at high risk of cardiac failure (ie those that have New York Heart Association Class I heart failure), troponin I (troponin T is allowed if the assay utilized can be verified to have cardiac specificity) and Nterminal of the prohormone brain natriuretic peptide (Nt-proBNP) levels will be evaluated at baseline in screening and every other cycle starting with cycle 2 and when clinically indicated. Any elevation in troponin or Nt-proBNP should be discussed with the study principal investigator prior to enrollment or treatment.
- Serum or urine β-HCG for females of childbearing potential
- Tumor restaging (within 6 weeks). This will consist of PET and CT scans (including neck, chest, abdomen/pelvis), which can be a combined study. MRIs may be used for patients in whom CT imaging is contraindicated.
- Tumor biopsy for biomarker studies (Section 9). An archival sample within 90 days and without intervening treatment is acceptable as the pre-treatment biopsy assuming that at least 15 unstained slides are available for evaluation.
- Stool sample for microbiome biomarker studies (Section 9)
- 12-Lead Electrocardiogram (EKG). A single 12-lead EKG will be done at screening in patients in cohorts A2, A3, and B2.
- Echocardiogram (TTE) or multigated acquisition (MUGA) scan: TTE or MUGA scan should be performed at screening for patients. All patients with an EF<50% must be discussed with the principal investigator prior to enrollment.

10.2 Required Data During Study

The following must be obtained during the study:

- Medical history, medication review, physical exam, and weight, ECOG performance status (see Appendix A)
- Toxicity assessment
- CBC with differential, blood chemistries including complete metabolic panel, phosphorus, magnesium, uric acid, LDH. These are required at each planned study visit during cycle 1 (C1D-6, C1D1, C1D2, C1D8, C1D15, C1D16) and on day 1 and day 15 of cycles 2-6. Patients do need to meet laboratory eligibility criteria on C1D-6.

- TSH, creatinine kinase, lipase, and triglycerides, as well as urine studies to include a urine dipstick for blood and protein and if positive a microscopic urinalysis and 24 hour urine collection (for protein) will be checked on day 1 of each cycle 1-6.
 - For patients assigned to cohorts A2, A3, and B2 with a previous history of anthracycline treatment and who are at high risk of cardiac failure (ie those that have New York Heart Association Class I heart failure), troponin I (troponin T is allowed if the assay utilized can be verified to have cardiac specificity) and Nterminal of the prohormone brain natriuretic peptide (Nt-proBNP) levels will be evaluated at every other cycle starting with cycle 2 and when clinically indicated. Any elevation in troponin or Nt-proBNP should be discussed with the study principal investigator prior to treatment.
- Pregnancy test at screening, C1D-6 (except for cohort A2a dose level 0), C1D2 (only for cohorts A1a, A1b, and B1), C1D15, and C2-6D1.
- Peripheral blood sample for biomarker studies before treatment on C1D-6 (for all cohorts except cohort A2a, dose level 0), C1D1, C1D2, C1D8, C1D15, C1D16, and on day 1 of C2-6 (Section 9).
- Tumor biopsy between C1D22 and C2D1.
- Tumor restaging: CT scans with PO and IV contrast of the chest, abdomen and pelvis (+/neck if involved at screening baseline) between C3D22 and C4D1. MRIs may be used for patients in whom CT scans are contraindicated.
 - Patients enrolled in cohort A2a, dose level 0, who have SD or PD on this scan have the option to remain on study and receive 4 weekly doses of rituximab during cycle 4 (days 1, 8, 15, and 22) while remaining the same dose and schedule of PF-04518600.
- Stool sample for biomarker studies between C1D22 and C2D1 using a home kit
- EKGs: Triplicate 12-lead EKGs will be done in cycle 1 in patients in cohorts A2, A3, and B2 on days when PF-04518600 is administered prior to administration. Triplicate 12-lead EKGs will be done on day 1 and 15 of cycles 2-6 in cohorts A2, A3, and B2 prior to therapy on those days. If the mean QTcF is prolonged (>501msec) immediate correction for reversible causes should be performed. If the QTc reverts to <501msec, and in the judgment of the investigator(s) and principal investigator is determined to be due to cause(s) other than investigational product, treatment may be continued with regular EKG monitoring. If in that timeframe the QTcF intervals rise above 501msec the investigational product will be held until the QTcF has not decreased to 480msec of less after 2 weeks, or if at any time a patient has a QTcF interval >515msec or becomes symptomatic, the patient will be removed from the study. Additional triplicate EKGs should be performed as clinically indicated (ie at the time of any cardiac or neurologic AE)
- Echocardiogram (TTE) or multigated acquisition (MUGA) scan: TTE or MUGA scan should be performed every 3 months while on therapy for patients in cohorts A2, A3, and

B2. All patients with an EF<50%, or a decrease from baseline EF of >10%, must be discussed with the principal investigator prior to treatment.

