Enrollment will begin with the phase 1 dose escalation stage to test the safety of these combinations in relapsed/refractory FL and to determine the recommended phase 2 dose (RP2D) to use for the phase 1b dose expansion cohorts as well as for the potential upfront cohorts. The cohorts in the phase 1 dose escalation stage will follow a 3+3 dose escalation schema, such that there will be a safety pause and evaluation after the first 3 patients at any given dose level have completed 6 weeks of therapy. If there are no dose limiting toxicities (DLTs) seen, the next dose level will open. If there is 1 DLT, an additional 3 patients will be enrolled at that dose level with a safety pause and evaluation after all 3 have completed 6 weeks of treatment. If there are 2 or more DLTs at any time in a given dose level, no further testing of that dose level will open. The next dose levels will follow the same 3+3 dose escalation schema (**Schema 1**). Once a recommended phase 2 dose is determined, this dose will be used in both the dose expansion cohorts as well as in the potential upfront dosing cohorts.

Enrollment will begin with cohorts A1a, dose level 1, and A2a, dose level 0 in an alternating fashion. Each subsequent cohort will be filled sequentially beginning with cohort A1a dose level 2, followed by cohort A2a dose level 1, then A2a dose level 2, then A3a dose level 1, and finally A3a dose level 2. If a patient is not eligible for the cohort that is being filled preferentially at the time of enrollment due to prior treatment history, they may be enrolled in the next cohort for which they are eligible. Note, if a patient in cohort A2a, dose level 0, has not had a response by the midtreatment response assessment following cycle 3, they will be allowed to received rituximab 375mg/m2 q7d for 4 weeks during cycle 4 (C4D1, C4D8, C4D15, C4D22).

Dose limiting toxicities (DLTs) are defined as any grade 3 or greater toxicity unless directly, and incontrovertibly, related to progressive disease with the exception of the following:

- Grade 3 hematologic abnormalities
- Grade 4 hematologic abnormalities that recover to grade 2 or lower with supportive treatment (including transfusion, IVIg, or growth factor) within 7 days
- Non-hematologic abnormalities:
 - Transient (≤ 24 hours) Grade 3 fatigue, local reactions, or headache that resolves to Grade ≤ 1 ;
 - Grade 3-4 nausea and vomiting controlled by optimal medical therapy within 72 hours;

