Toxicity will be continuously monitored and recorded using CTCAE 4 criteria, up to 30 days following the last dose of the study treatment or until resolution of toxicity to grade 1 or baseline, whichever occurs last. Response will be assessed 4-6 weeks after the completion of therapy (either after cycle 6 of therapy for patients who complete the planned cycles of therapy, or after their last dose of treatment for patients who discontinue treatment before cycle 6) by PET and CT scans of the neck (if involved at baseline), chest, abdomen, and pelvis, as well as at 6, 12, and 18 months from the end of treatment (+/- 2 weeks) in the absence of disease recurrence or progression (PET may be omitted once patient is in CR). In addition, CT scans of the chest, abdomen, and pelvis +/- neck will be obtained 4 weeks (+/- 1 week) after the completion of cycle 3 while on therapy. If patients experience evidence of progressive disease confirmed by imaging while on treatment, they will be allowed to complete treatment if they meet the definition of an indeterminate response according to LyRIC criteria.²

Expected toxicities and potential risks for all drugs are described in Section 6 (Dosing Delays/Dose Modifications). No investigational or commercial agents or therapies other than those described below may be administered with the intent to treat the participant's malignancy.

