5.4 Criteria for Taking a Participant Off Protocol Therapy

Duration of therapy will depend on individual response, evidence of disease progression and tolerance. In the absence of treatment delays due to adverse event(s), treatment may continue for 25 weeks or until one of the following criteria applies:

- Disease progression
- Intercurrent illness that prevents further administration of treatment
- Unacceptable adverse event(s)
- Participant demonstrates an inability or unwillingness to comply with the oral medication regimen and/or documentation requirements
- Participant decides to withdraw from the protocol therapy
- General or specific changes in the participant's condition render the participant unacceptable for further treatment in the judgment of the treating investigator

Participants will be removed from the protocol therapy when any of these criteria apply. The reason for removal from protocol therapy, and the date the participant was removed, must be documented in the case report form (CRF). Alternative care options will be discussed with the participant.

When a participant is removed from protocol therapy and/or is off of the study, the relevant Off-Treatment/Off-Study information will be updated in OnCore.

5.5 **Duration of Follow Up**

Patients who complete treatment or come off treatment for reasons other than progressive disease (PD) will have active follow up through 24 months or until death, PD, or next treatment, whichever comes first. After 24 months, PD, or next treatment, patients will enter survival follow up. Participants removed from protocol therapy for unacceptable adverse event(s) will be followed until resolution or stabilization of the adverse event.

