8.2 Other Agent(s)

8.2.1 Rituximab

Single agent monoclonal antibodies are an attractive treatment option given excellent tolerability. Rituximab is approved as a single agent in relapsed or refractory FL and in combination with chemotherapy for first line therapy of FL.⁵¹

Rituximab is a genetically engineered, chimeric, murine/human monoclonal antibody directed against the CD20 antigen found on the surface of normal and malignant pre-B and mature B cells. The antibody is an IgG1 κ immunoglobulin containing murine light and heavy-chain

variable region sequences and human constant region sequences. Rituximab is composed of two heavy chains of 451 amino acids and two light chains of 213 amino acids (based on cDNA analysis) and has an approximate molecular mass of 145 kD. Rituximab has a binding affinity for the CD20 antigen of ~8.0 nM. Several mechanisms of action have been proposed in various models including complement-dependent cytotoxicity (CDC), antibody-dependent cell-mediated cytoxicity (ADCC), induction of apoptosis, and a "vaccinal" effect.⁵² It is likely that rituximab works through a combination of these mechanisms.

The objective response rate for rituximab monotherapy in relapsed low-grade B-cell lymphoma is approximately 24-36% with complete response rates of approximately 7%.⁵³ Several mechanisms for rituximab resistance have been proposed including variable CD20 expression by lymphoma subtype, variability in complement activation, and polymorphisms in Fc receptors.⁵⁴⁻⁵⁶ Novel agents that overcome these resistance mechanisms might offer similar complete response rates to combined chemotherapy and immunotherapy with improved tolerability.

Rituximab monotherapy has been evaluated in the upfront therapy as well. When given as 4 weekly infusions to patients who would otherwise have undergone observation, the objective response rate was 72% and the median time to progression was 2.2 years.⁵¹ The addition of maintenance rituximab, given once every 8 weeks for 4 treatments, to patients with at least stable disease following induction therapy with rituximab monotherapy is associated with an improvement in event free survival (24 versus 13 months, <0.001).⁵⁷

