¹ See Sections 10.1 and 10.2. All tests will be required at screening and tumor lysis labs (CMP, uric acid, LDH, phosphorus) will be repeated at each study visit in cycle 1. Patients do need to meet laboratory eligibility criteria on C1D-6

²Consisting at a minimum of hepatitis C antibody, hepatitis B surface antigen and hepatitis B core antibody.

³ See Sections 10.1, 10.2, and 10.3. Note, patients with SD or PD at midtreatment CT scans restaging after cycle 3 will have the option to stay on study and received 4 weekly infusions of rituximab 375mg/m2 during cycle 4 (days 1, 8, 15, and 22) while continuing PF-04518600 at the same dose and schedule.

⁴ One pretreatment peripheral blood sample(s) will be collected for correlative studies (Section 9) before treatment on C1D1, and then before treatment C1D2, C1D8, C1D15, C1D16 and on day 1 of cycles 2-6, at the end of treatment visit and at every other follow-up visit beginning 6 months (+/- 2 weeks) from the end of treatment and then every 6 months (+/- 2 weeks) until 24 months from the end of treatment.

⁵ A bone marrow biopsy done will be required at the end of treatment if a PET/CT scan shows a complete metabolic response to confirm a complete response.

⁶On treatment tumor biopsy will be done between C1D22 and C2D1. A tumor biopsy will also be done at the time of disease progression.

⁷ Stool studies will be collected during Screening, between C1D22 and C2D1, and at the completion of therapy by patient at home using kit provided by the research staff.

⁸ EKGs (single EKG at screening and then triplicate EKGs for all subsequent EKGs) will be performed for patients in cohorts A2, A3, and B2 at screening, on each day of administration of PF-04518600 and at the EOT visit.

⁹ TTE/MUGA will be performed at screening and every 3 months on treatment and when clinically indicated.

 10 EOT = end of treatment, to take place 4-6 weeks from the last dose of study treatment.

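### A2a dose level 0: the option to add rituximab after progression conflicts with Sections 5.4 and 5.1, its trigger scan has two timings, and later responses are not separated from single-agent ones

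*Combined protocol and SAP*

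**What the plan says.** Dose level 0 of cohort A2a is the only level in the trial with no planned rituximab (Sections 5.1 and 5.2.1). Section 5.1 offers rituximab in cycle 4, on days 1, 8, 15 and 22, to a level 0 patient who "has not had a response by the midtreatment response assessment following cycle 3"; Section 5.2.2 repeats this. Section 10.2 spells out the group: "Patients enrolled in cohort A2a, dose level 0, who have SD or PD on this scan have the option to remain on study" and take the four weekly rituximab doses. Footnote 3 of the level 0 study calendar agrees: "patients with SD or PD at midtreatment CT scans restaging after cycle 3 will have the option to stay on study".

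On progression, Section 5.4 lists it among the reasons for stopping and adds: "Participants will be removed from the protocol therapy when any of these criteria apply". Section 5.1 says of patients whose progression is confirmed by imaging on treatment that "they will be allowed to complete treatment if they meet the definition of an indeterminate response according to LyRIC criteria".

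On timing of response, Section 5.1 states: "Response will be assessed 4-6 weeks after the completion of therapy". It also sets a CT at 4 weeks (+/- 1 week) after cycle 3 is completed, whereas Section 10.2 sets that CT between C3D22 and C4D1. Section 13.1 names the CR rate as a primary endpoint without reference to dose level, and Section 13.3 analyses all evaluable patients.

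**The concern.** A site with a level 0 patient in progression finds one section offering continued treatment plus a new drug and another calling for removal, with no cross-reference between them. Under Appendix C (Section 3.8.2), a departure that was not prospectively approved is a protocol violation, so the same decision could be recorded as compliant or as a violation depending on the section consulted.

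Level 0 is also the one place where the activity of PF-04518600 without rituximab can be seen. The background section raises this very attribution problem for rituximab plus pidilizumab. If end-of-treatment response is tabulated for level 0 as a single group, it pools patients observed on PF-04518600 alone with patients observed on PF-04518600 plus rituximab, and a response produced by rituximab can be read as single-agent activity.

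**Working it through.** **1. The progression rules side by side**

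| Level 0 patient at the mid-treatment scan | Section 5.4 | Section 5.1, sentence on progression | Section 10.2 and calendar footnote 3 |
|---|---|---|---|
| Stable disease | stays on | does not apply | may stay and add rituximab |
| Progression, LyRIC indeterminate | off therapy, if this counts as progression (5.4 names no criteria) | may complete treatment | may stay and add rituximab |
| Progression, not indeterminate | off therapy | no permission given | may stay and add rituximab |

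The last row conflicts with both 5.4 and the 5.1 sentence; the middle row conflicts at most with 5.4. Part of the tension lies inside 5.1, whose own description of the option covers every patient without a response.

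**2. The scan that triggers the option**

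A cycle is 28 days. Counting from the last day of cycle 3, 4 weeks (+/- 1 week) is 21 to 35 days later, that is C4D21 to C5D7. Rituximab would have started on C4D1, and the day 1, 8 and 15 doses would precede even the earliest date. Counting from the last planned dose of cycle 3 (C3D15) gives C4D8 to C4D22, still after C4D1. Only the Section 10.2 window precedes rituximab.

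**3. Does the part A efficacy rule move?**

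The rule is at least 3 CRs in 15, with a null rate of 5% and an alternative of 30% (Section 13.2). Exact binomial: P(X >= 3 | 15, 0.05) = 0.0362 (stated 4%) and P(X >= 3 | 15, 0.30) = 0.8732 (stated 87%). The plan's figures are reproduced. The 15 are patients at the RP2D. Section 13.2.1 read alone does not exclude level 0 as the RP2D, but Schema 1 names only levels 1 and 2, and Section 5.1 defines A2b as the triplet. Level 0 patients are therefore not among the 15.

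**4. How much could rituximab add to the level 0 response count?**

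Inputs from the protocol: rituximab alone in relapsed low-grade B-cell lymphoma has an objective response rate of "approximately 24-36% with complete response rates of approximately 7" percent (Section 8.2.1); level 0 has 3 or 6 patients under the 3+3 scheme. Assumptions, because the documents give neither: q, the true PF-04518600-alone response rate, and u, the share of non-responders who take rituximab.

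With q = 0, the chance of at least one reported response is 1 - (1 - u x r)^n, where r is the rituximab rate. For example, with u = 1, r = 0.24 and n = 3: 1 - 0.76^3 = 0.561.

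| At least one | u | n = 3 | n = 6 |
|---|---|---|---|
| Objective response (r = 0.24 to 0.36) | 100% | 56-74% | 81-93% |
| Objective response | 50% | 32-45% | 54-70% |
| CR (r = 0.07) | 100% | 20% | 35% |
| CR | 50% | about 10% | about 19% |

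If the agent is active, the expected rate as reported is q + (1 - q) x u x r. With q = 10% and u = 100% this is 0.10 + 0.90 x 0.24 = 31.6% to 0.10 + 0.90 x 0.36 = 42.4%, against a true single-agent rate of 10%. With a cut-off before rituximab, the carry-over is zero.

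**The case against.** The case against is substantial on the statistical side.

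- No PF-04518600-alone response rate is an endpoint. Section 1.2 asks about immunotherapy combined with rituximab, and Section 13.1 names no monotherapy response. A reader might infer that the primary CR test is biased; step 3 shows that it is not. This stands, and it limits the response point to descriptive reporting.
- The single-agent result is not lost. On the Section 10.2 timing, only patients already documented with stable or progressive disease can add rituximab, so each is a known non-responder beforehand. This also stands, but the plan does not say that the information will be used, and on the Section 5.1 timing that documentation would come too late.
- A reader might infer that a site cannot satisfy Sections 5.4 and 10.2 together. That goes too far: 10.2 offers an option, and a patient who does not take it breaches neither. Section 5.1 also does not say that indeterminate response is the only route to completing treatment.
- Section 10.2 and the footnote may be meant as a cohort-specific exception to the general list in 5.4. That is plausible, but 5.4 contains no exception and nothing points from one to the other.
- The probabilities at full uptake are a worst case, which is why half uptake is shown. Transfer of the rituximab rates is also an assumption: part A admits patients refractory after anti-CD20 therapy (Section 3.1.1), and the source rates are for relapsed low-grade lymphoma generally.

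**Conclusion.** The point holds on three counts.

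The progression rules conflict whenever a level 0 patient with progression takes the rituximab option: with Section 5.4 as written, and with the Section 5.1 sentence when the progression is not LyRIC indeterminate. The two timings of the mid-treatment CT cannot both serve a decision due on C4D1. End-of-treatment response at level 0 can include responses reached after the added rituximab, because Sections 11.1, 13.1, 13.2 and 13.3 contain no rule that separates them.

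The first two affect what sites do. The third is a smaller matter: it concerns the description of 3 or 6 patients and no go/no-go rule. Its size depends on uptake and on the assumed rituximab rates, as tabulated, and the tabulated probabilities also assume an inactive agent. The absence of a rule is judged on the available text, which lacks whatever lies between the opening line of Section 13.3 and Section 14.

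**What to change.** - Reconcile Sections 5.4 and 5.1 with Section 10.2 and footnote 3 of the level 0 calendar for patients with progression, and cross-refer. Which clinical rule applies is for the sponsor to decide.
- Give the mid-treatment CT one timing in Sections 5.1 and 10.2, so that it is clear whether the scan precedes the cycle 4 decision.
- In Sections 11.1 and 13.1, state that single-agent response at level 0 is the best response up to the last assessment before the first rituximab dose; that patients who add rituximab count as non-responders to monotherapy; and that their later responses are listed separately as PF-04518600 plus rituximab.

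The cost is a few sentences. No new assessment is needed if the CT falls before rituximab, as in Section 10.2. There are three drawbacks. The pre-rituximab assessment is CT without PET, so it is not equivalent to a CR confirmed by PET and marrow at end of treatment. Patients who add rituximab contribute three cycles of monotherapy observation where others contribute up to six. The reported level 0 response rate may be lower.
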